7.9.1.2.3. Assessing Effect of Dose Change

Sensitivity analyses of the effect of dose change on clinical outcomes will be conducted. An NCS analysis will be performed separately on the PACC and other clinical measures after censoring all observations after the dose increase (that is, after the first dose of 800 mg). In other words, clinical measures will be included only through the last available value prior to first dose

escalation for each participant. The model and variables included in the NCS analysis will be the same as specified in Section 7.9.1.1. The null hypothesis is that the treatment difference between solanezumab and placebo for the PACC score is equal to zero. Since the timing (visit) of dose escalation will vary for each participant, a specific endpoint for comparison between treatment groups will not be available. Therefore, the hypothesis will be tested using the p-value obtained for the overall treatment effect.

7.9.1.2.4. Assessing Effect of Exposure

Additionally, we will implement a sensitivity analysis to estimate the potential differences in the cumulative treatment exposure over time due to both the dose increase and the COVID-19 hiatus. In addition to the two spline basis expansion terms for time from baseline in the primary analysis NCS model, this model will also include spline basis expansion terms for the cumulative exposure to solanezumab over time. The fixed effects will include the following terms: (i) NCS basis expansion terms for time (two terms), (ii) NCS basis expansion terms for cumulative exposure (two terms), (iii) PACC test version administered, (iv) age, (v) education, (vi) APOE4 Carrier Status (yes/no), and (vii) baseline florbetapir cortical SUVr. Treatment group is not explicitly included in the model, but the cumulative exposure for the placebo group is set to zero. Based on this model, we will be able to visualize the modeled mean for the PACC over time with 95% confidence intervals for (i) placebo group, (ii) the low-dose per-protocol exposure, and (iii) the high-dose per-protocol exposure. We will also be able to visualize the modelled mean PACC at 240 weeks for the observed range of cumulative dose exposure and identify the minimum exposure at which the 95% confidence interval excludes the mean for the placebo group.

To further investigate exposure, participants will be grouped into one of three exposure groups based on the tertiles of the distribution of cumulative exposure to either solanezumab or placebo: low exposure, medium exposure, and high exposure. Within these exposure groups, solanezumab-treated participants will be compared to placebo-treated participants using the NCS model including effects for (i) NCS basis expansion terms, (ii) exposure group (iii) NCS basis expansion terms-by-treatment-by-exposure group interaction, (iv) PACC test version administered, (v) age, (vi) education, (vii) APOE4 Carrier Status (yes/no), and (viii) baseline florbetapir cortical SUVr. This model will constrain the baseline treatment group means to be the same within exposure group, but allow different baseline means between the exposure groups. The interaction will be tested by likelihood ratio test comparing the full model to the reduced model without any exposure group interaction effects.

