9.1. Treatments Administered

This study was initiated as a comparison of solanezumab 400 mg compared with placebo. The active drug group was given an IV infusion of solanezumab 400 mg once every 4 weeks. The study protocol was amended to increase the dose; subjects will be escalated to 800 mg Q4W for at least 2 infusions, and then 1600 mg Q4W until the conclusion of the treatment, as described below (Table A4.1). Dosing should be once every 4 weeks; a minimum of 14 days between infusions is required.

Table A4.1. Treatment Regimens

Regimen	Dose from Visit 6 (Week 0) through Visit 65 (Week 236), Placebo-Controlled Period
Solanezumab	
 • 400 mg IV infusion every 4 weeks for at least 2 doses^a, and then: • 800 mg IV infusion every 4 weeks for at least 2 doses, and • 1600 mg IV infusion every 4 weeks through Week 236
Placebo	sterile saline solution (0.9% sodium chloride) IV infusion every 4 weeks (infusion volumes to increase accordingly with dose escalation paradigm as described in the operations manual)
Dose from Visit 66 (Week 240) through Visit 116 (Week 440), Open-Label Period	
Early-start solanezumab ^b	1600 mg IV infusion every 4 weeks through Week 440 ^c
Delayed-start solanezumab ^b	
 • 400 mg IV infusion every 4 weeks for at least 2 doses^{a, c}, • 800 mg IV infusion every 4 weeks for at least 2 doses^c, and • 1600 mg IV infusion every 4 weeks through Week 440^c

Abbreviation: IV = intravenous.

^a Subjects who initiated the study before the implementation of amendment (d) may have more than 2 doses of 400 mg Q4W.

^b “Early-start solanezumab” refers to the treatment regimen received by subjects randomized to solanezumab in the placebo-controlled period who continue to receive solanezumab in the open-label period. “Delayed-start solanezumab” refers to the treatment regimen received by subjects randomized to placebo in the placebo-controlled period who switch to solanezumab treatment in the open-label period.

^c Subjects who are receiving 400 mg Q4W or 800 mg Q4W when they complete the placebo-controlled period may be maintained at that dose in the open-label period.

Changes in the escalation schedule may be made at the investigator’s discretion with the notification of a Medical Monitor.

The investigator or his/her designee is responsible for the following:

- Explaining the correct use of the investigational agent(s) to the site personnel

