6.1. Summary of Study Design

Study A4 is a multicenter, randomized, double-blind, placebo-controlled, Phase 3 study comparing solanezumab with placebo for 240 weeks in approximately 1150 participants ages 65 to 85 years old with preclinical AD, defined as having evidence of brain amyloid pathology without clinically evident cognitive impairment at screening. Participants who met entry criteria were randomized in a 1:1 ratio (approximately 575 per treatment arm) to solanezumab or placebo once every 4 weeks. Participants were randomized within the site by education – high (13 or more years) or low (12 or less years) and the presence of one or more apolipoprotein E gene (APOE) ϵ 4 alleles (yes, no). The primary hypothesis being tested is that the cognitive decline at the end of the placebo-controlled period will be significantly less for solanezumab than for placebo. Participants completing the placebo-controlled period of the study can opt to participate in the open-label period of the study that will last for up to 204 weeks or until the primary analyses of the placebo-controlled period of the study are completed and reviewed.

At the beginning of the COVID-19 pandemic, a hiatus was implemented to allow participants to pause study activities without missing visits and resume when COVID safety mitigations were in place (for example, vaccines, home infusions, etc.). The hiatus extended the end of the placebo-controlled period for up to 9 months and the placebo-controlled period will be administratively closed in December 2022.

Figure A4.SAP.1 illustrates the study design.

Abbreviation: V = visit.

Figure A4.SAP.1. Illustration of study design for Clinical Protocol A4.

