6.2. Determination of Sample Size

In order to develop an appropriate measure of cognitive decline in a preclinical population, we tested several combinations of measures using data from longitudinal studies in clinically normal populations, including the ADNI; the AIBL; the ADCS-PI trial; and the HABS.

Sample size and power at 4.5 years (240 weeks) for the PACC were estimated using data from ADNI and HABS. Estimates were obtained by applying appropriate assumptions regarding treatment difference, SD, and attrition for a 4.5-year study in a preclinical AD population. In ADNI, the difference in the composite change between participants with and without elevated brain amyloid at 240 weeks was 2.13 (SD=2.85). Similarly, in HABS, the difference in the composite change between participants with and without elevated brain amyloid at 240 weeks was 2.66 (SD=3.08). Given the ADNI-derived estimate of SD at 240 weeks of SD=2.85 and 30% attrition, the total N=1150 provides 80% power (5% 2-sided alpha) to detect a treatment difference of 0.532 points or $0.532/2.13 = 24.9\%$ of the amyloid group difference. Similarly, based on the HABS estimate of SD at 240 weeks of SD=3.08, the study has 80% power to detect a treatment difference of 0.570 points or $0.570/2.66 = 21.4\%$ of the amyloid group difference.

For the open-label period, the estimated mean PACC difference between cognitively normal participants with and without elevated brain amyloid at 336 weeks is 2.95 (SD=3.77) based on ADNI and 4.74 (SD=3.99) based on HABS. Accounting for the administrative censoring that will be induced by the common close design of the open-label period, and assuming an overall attrition rate of 30%, about 266 PACCs are expected to be available at 336 weeks. The visit-to-visit correlation is estimated to be about 0.5. Under these pilot estimates, 266 PACCs at 336 weeks would provide 80% power to detect a randomized group (early-start vs delayed-start treatment with solanezumab) difference of about 0.9 PACC points. This change of 0.9 PACC points reflects 30% of the difference between amyloid-positive and -negative participants based on ADNI, and 20% of that difference based on HABS.

Sample size for the study was determined assuming an MMRM analysis prior to the interruption caused by the COVID-19 pandemic. Applying the NCS approach in simulated trials with a COVID-19 pandemic interruption suggests the study has 94% power to detect an effect size of 0.75 PACC points at 240 weeks.

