7.9.3.4. Other Analyses of the Open-Label Period

Additional descriptive analyses of the OLE data will include (1) an extension of the primary analysis NCS model respecting the blinded-phase randomized group assignments; and (2) an extension of the exposure adjusted model (Section 7.9.1.2.4).

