7.13.1.3. Analyses of TEAEs by Dose

For participants treated with solanezumab, summaries of treatment-emergent adverse events will be displayed with events assigned to the dose (400 mg versus 1600 mg for participants assigned to solanezumab, with events occurring at the 800 mg level assigned to the 1600 mg group, and low dose placebo and high dose placebo for participants assigned to placebo based on the blinded dose level) that the participant was taking at the time of the event. At the first occurrence of a high dose for a participant, all subsequent observations will also be considered as high dose. Events will be reported as frequencies and rates, adjusted for the amount of time until the event for participants who experienced the event or total time on the specified dose for those who did not experience the event. Treatment-emergence will be defined separately for each dose level, with the time period immediately preceding the dose as the baseline period. An adverse event that first appears or worsens in severity subsequent to the dose will be considered treatment-emergent.

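### The spline exposure model in SAP 7.9.1.2.4 codes placebo exposure as zero, so its per-protocol curves and minimum-exposure reading mix any drug effect with non-random attendance and escalation timing

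*SAP*

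**What the plan says.** SAP 7.9.1.2.4 plans two sensitivity analyses of PACC by cumulative exposure, motivated by the dose increase and the COVID-19 hiatus.

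- **Spline model.** It has two spline terms for time, two for cumulative solanezumab exposure, and the usual covariates. On the arms it says: "Treatment group is not explicitly included in the model, but the cumulative exposure for the placebo group is set to zero". It yields PACC curves for placebo and for the low-dose and high-dose regimens taken per protocol, modelled PACC at 240 weeks across the exposure range, and the smallest exposure whose 95% interval leaves out the placebo mean.
- **Tertile model.** The next paragraph groups participants by "tertiles of the distribution of cumulative exposure to either solanezumab or placebo" and compares the arms within each group, with a likelihood ratio test of interaction.

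A placebo exposure history exists. Protocol Table A4.1 provides for placebo "infusion volumes to increase accordingly with dose escalation paradigm", Protocol 9.8 has missed and incomplete infusions recorded, and SAP 7.13.1.3 classifies events by "low dose placebo and high dose placebo for participants assigned to placebo based on the blinded dose level".

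Exposure is not randomized. Protocol 7.1.4 and 9.1 leave delays and changes in escalation to the investigator, Protocol 9.8 anticipates missed infusions, and SAP 6.1 describes the hiatus.

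**The concern.** With placebo fixed at zero and no treatment term, the exposure coefficients are the only place where the arms can differ. Those coefficients are estimated from differences among solanezumab participants in how much drug they accumulated. If people who decline more slowly also attend more, high exposure marks slower decliners whether or not the drug works. The placebo arm has the same attendance pattern and could be used to subtract it, but the model averages placebo over good and poor attenders.

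At stake are the two outputs that only this model produces: the per-protocol curves and the minimum exposure that separates from placebo. With an inert drug, either could look like a dose-related benefit.

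**Working it through.** **1. Scale.** Section 7.9.1.2.4 states no figure, so I take the scale from elsewhere in the SAP. SAP 6.1 allocates about 575 participants to each arm. SAP 6.2 says "the total N=1150 provides 80% power (5% 2-sided alpha) to detect a treatment difference of 0.532 points"; its inputs are an ADNI-based SD of 2.85 and attrition of 30%.

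Power = Φ(Δ / (SD·√(2/n)) − 1.960).

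- n = 575/1.3 = 442.3 per arm: SE = 2.85·√(2/442.3) = 0.1916; Φ(2.776 − 1.960) = 79.3%, which matches the stated 80%.
- n = 575 × 0.7 = 402.5 per arm: SE = 0.201; power 75.4%; detectable difference 2.80 × 0.201 = 0.563.

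The stated MMRM basis may account for the gap between the two. Here 0.532 serves only as a yardstick.

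**2. Where the curve is read.** Week 0 to Week 236 every 4 weeks is 236/4 + 1 = 60 infusions.

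- Low dose: 60 × 400 mg = 24.0 g.
- High dose on the shortest schedule: 2 × 400 + 2 × 800 + 56 × 1600 = 92,000 mg = 92.0 g.

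In simulation with 15% missed and everyone escalated at week 8, mean solanezumab exposure is 77.2 g and the 90th percentile 90.8 g. With 8% missed and spread escalation these are 63.7 g and 82.8 g. So 92.0 g describes the most complete attenders.

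**3. Direction.** With no drug effect, reading the model at exposure e against placebo targets E[PACC | exposure = e] − E[PACC]. This is zero only if exposure and decline are unrelated. Comparing the arms at the same assigned exposure targets E[PACC | e, solanezumab] − E[PACC | e, placebo]. The selection then cancels, provided treatment does not itself change attendance.

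**4. Size.** Simulation with no drug effect:

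- From the documents: 575 per arm, SD of change 2.85, 30% attrition, PACC every 24 weeks to Week 240.
- Assumed: random dropout, share of infusions missed, escalation timing, correlation (rho) between attendance and individual slope, random intercept-and-slope covariance (treated as known), and an exposure knot at the median of non-zero exposures.
- 300–400 runs per setting. At 300 runs the Monte Carlo error of a 5% rate is √(0.05 × 0.95/300) = 1.3 percentage points.

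Results for the spline model at 92.0 g, as bias in PACC points / share of runs whose 95% interval excludes placebo:

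| Missed; escalation | rho 0 | rho 0.1 | rho 0.2 | rho 0.3 |
|---|---|---|---|---|
| 8%; weeks 8–156 | 0.00 / 6% | +0.04 / 4% | +0.12 / 6% | +0.18 / 14% |
| 15%; weeks 8–156 | −0.02 / 3% | +0.09 / 6% | +0.19 / 15% | +0.27 / 21% |
| 15%; all at week 8 | – | +0.08 / 7% | +0.18 / 17% | +0.28 / 32% |
| 25%; weeks 8–156 | – | +0.16 / 11% | +0.30 / 20% | +0.49 / 49% |

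The 25% row is a stress case. As an average it exceeds 10/60 = 17%, the cumulative level at which Protocol 9.8 allows discontinuation. A separate simulation with about 10% missed and rho 0.20 gave +0.11, in line with the 8% row.

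**5. Alternatives on the same simulated data** (15% missed, weeks 8–156, rho 0.2):

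| Analysis | Bias | Interval excludes zero |
|---|---|---|
| SAP spline model | +0.19 | 15% |
| Placebo exposure counted, exposure-by-treatment terms | 0.00 | 5.8% |
| SAP tertile comparison, top tertile | +0.01 | 5.0% |
| Primary contrast | 0.00 | 4.8% |

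Across all settings with rho 0.1–0.3, the second and third analyses stay within 0.04 points of zero, with rejection of 3–7%.

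**The case against.** Much of the opposing case stands, and it limits the point.

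- **A reader might infer that the SAP's exposure assessment has no placebo control.** It has one. The tertile paragraph compares arms at similar exposure and is not misled in simulation. SAP 7.15 adds a marginal structural dose model weighted for non-random dosing and dropout.
- **A reader might infer that this is the plan's main test of the dose increase or hiatus.** No section ranks it so. SAP 7.4 makes everything secondary to the primary analysis, and SAP 7.9.1.2.3 separately censors at escalation. The primary contrast is unaffected.
- **A reader might infer that the open-label extension in SAP 7.9.3.4 inherits the flaw.** That work is described as descriptive, and the former placebo arm then receives solanezumab, so exposure no longer varies in one arm only.
- **The outputs are mostly displays.** No test is specified at high-dose per-protocol exposure. The minimum-exposure reading, however, does rest on an interval excluding placebo.
- **The size is uncertain.** The documents give neither a missed-infusion rate nor a link between attendance and decline. Some exposure variation is administrative, such as enrolment before amendment (d) or the hiatus. With few misses and a weak link the bias is small: +0.04 and 4% at 8% missed and rho 0.1.

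None of this corrects the curves or the minimum exposure, which come only from the spline model. Nor does the SAP say which analysis governs if the spline and tertile results disagree.

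**Conclusion.** The flaw is real but confined to the spline model's per-protocol curves and minimum-exposure reading, so its severity is minor. With an inert drug, 8–15% of infusions missed, rho 0.1–0.3 and escalation spread over weeks 8 to 156, the spurious benefit is about 0.04–0.27 PACC points. That is 0.04/0.532 = 8% to 0.27/0.532 = 51% of the planned detectable difference. The 95% interval excludes placebo in about 4–21% of runs against a nominal 5%. If everyone escalated at week 8 with 15% missed, the upper end becomes 0.28 points and 32%. With no link the bias is about zero.

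The direction follows from the model as written, given a link between attendance and slower decline. The size depends on the assumptions listed, which the documents neither support nor exclude.

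**What to change.** In the placebo-controlled-period spline model:

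1. Give every participant in both arms a cumulative assigned exposure: blinded dose level times completed infusions.
2. Fit NCS(time) + NCS(assigned exposure) + NCS(assigned exposure)-by-treatment + the listed covariates. With a boundary knot at zero exposure, the arms still coincide at baseline.
3. Base the per-protocol curves and the minimum-exposure reading on solanezumab versus placebo at the same assigned exposure.
4. State the exposure knots. The SAP does not, and with placebo coded zero about 56% of simulated observations are zero, so a knot at the overall median would fall on the boundary.

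At minimum, base exposure conclusions on the tertile comparison already planned and drop the minimum-exposure reading.

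**Cost.** SAP wording and two more fixed-effect terms, on data already held. The standard error of the exposure contrast rose from 0.236 to about 0.256 (0.256/0.236 = 1.08) in one simulation and from 0.215 to 0.226 (1.05) in another. The result remains a non-randomized sensitivity analysis. It conditions on exposure after randomization and assumes that treatment does not itself change attendance, which these simulations did not test.

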7.1. General Considerations

Unless otherwise noted, all tests of treatment effects will be conducted at a 2-sided alpha level of 0.05; 2-sided confidence intervals will be displayed with a 95% confidence level. All tests of interactions between treatment and other factors will be conducted at an alpha level of 0.05.

All analyses will follow the modified intent-to-treat (mITT) principle unless otherwise specified. An ITT analysis is an analysis of data by groups to which the participants are assigned by random allocation, even if the participant does not take the assigned treatment, does not receive the correct treatment, or otherwise does not follow the protocol. An mITT analysis is an ITT analysis for all participants who have a baseline and at least 1 postbaseline measure. All safety analyses will be done using the safety population. Analysis populations are described below (Section 7.5).

When change from baseline is assessed, participants will be included in the analysis only if both a baseline and a post-baseline measure are available. Unless otherwise defined, a baseline measure is the last non-missing observation collected prior to the first infusion of study medication. End point is the last non-missing post-baseline measurement.

For MMRM analyses, observations collected at non-scheduled visits (see Section 7.2) will not be included in the analyses. For NCS and MMRM analyses, unless otherwise specified, an unstructured covariance structure will be used. If the unstructured covariance structure matrix results in a lack of convergence, the following covariance structures will be used in sequence: heterogeneous Toeplitz covariance structure, heterogeneous autoregressive covariance structure, heterogeneous compound symmetry covariance structure and homogeneous compound symmetry covariance structure.

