7.9. Efficacy Analyses

7.9.1. Analysis of Primary Outcome (Placebo-Controlled Period)

7.9.1.1. NCS Analysis of Primary Outcome

The primary objective of this study is to test the hypothesis that intravenous infusion of solanezumab will slow cognitive decline in preclinical AD as compared with placebo.

The original mITT analysis (that is, all participants as randomized to treatment who have a baseline and at least 1 postbaseline measure) for the primary outcome will be retained and conducted at the end of the treatment period, although the dose was increased during the study and dosing and assessments were interrupted due to COVID-19; in other words, the primary analysis will include all data for the solanezumab group as the treatment group versus placebo. As with the original analysis plan, the hypothesis for this analysis will be tested against a two-sided alpha level of .05.

The details of this analysis including the analytic method and model are presented below.

An NCS analysis with 2 degrees of freedom will be used to assess the difference between treatment groups in change from baseline for the PACC score at 240 weeks. The composite score at baseline and each post-baseline visit will be the dependent variable. Time will be treated as a continuous variable with values equal to the years between baseline and follow-up exam dates. We will assume an unstructured covariance structure, where the time values are mapped back to the corresponding visits. The NCS basis expansion will assume an interior knot at the median of observation times, and boundary knots at zero years and the maximum follow-up (Hastie 1992). The fixed effects will include the following terms: (i) NCS basis expansion terms (two terms), (ii) NCS basis expansion terms-by-treatment interaction (two terms), (iii) PACC test version administered, (iv) age, (v) education, (vi) APOE4 Carrier Status (yes/no), and (vii) baseline florbetapir cortical SUVr. The model is constrained to not allow a difference between treatment group means at baseline.

The null hypothesis is that the treatment difference between solanezumab and placebo for the PACC score at 240 weeks is equal to zero. The primary analysis will be carried out in the mITT population that is randomized and has a baseline score and at least 1 post-baseline assessment. If the unstructured covariance structure matrix results in a lack of convergence, the following structures will be used in sequence:

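### The minimum-exposure readout in SAP 7.9.1.2.4 sets the interval of one modelled mean against the placebo estimate, so it is not a 5% comparison and its error varies with exposure

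*SAP*

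**What the plan says.** SAP 7.9.1.2.4 replaces the treatment terms of the primary spline model with a two-term natural cubic spline in cumulative solanezumab exposure. On coding it says: "Treatment group is not explicitly included in the model, but the cumulative exposure for the placebo group is set to zero". Two displays follow. The first is to "visualize the modeled mean for the PACC over time with 95% confidence intervals for (i) placebo group" and for two per-protocol exposure profiles. The second is to "visualize the modelled mean PACC at 240 weeks for the observed range of cumulative dose exposure", from which the analyst will "identify the minimum exposure at which the 95% confidence interval excludes the mean for the placebo group".

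Every interval named in that paragraph belongs to a modelled mean. It mentions no contrast with placebo, standard error of a difference, simultaneous band or multiplicity step. SAP 7.1 sets the general convention: "2-sided confidence intervals will be displayed with a 95% confidence level", alongside 2-sided tests at 0.05. For the primary model, which this one adapts, SAP 7.9.1.1 states: "The composite score at baseline and each post-baseline visit will be the dependent variable". The modelled means are therefore PACC levels, not changes.

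**The concern.** Asking whether the interval of one estimate covers the point estimate of another is not a test of their difference. Two errors act in opposite directions:

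- The placebo mean is itself estimated (the plan gives it its own interval), and the rule treats it as known. This makes the rule too loose.
- The interval of the modelled mean carries uncertainty in the intercept and the common time curve. The same uncertainty sits in the placebo mean and cancels in the difference. This makes the rule too strict.

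Which error dominates depends on exposure. The output is a threshold, so both matter. Where the rule is strict, a real effect at low exposure can go unflagged and the reported minimum moves up. Where it is loose, noise is more easily reported as an effective exposure. In both cases the threshold partly reflects the variance structure. A reader who sees a 95% interval exclude the placebo mean will assume the usual 5% standard of SAP 7.1.

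**Working it through.** **Stated figure.** The documents give no error rate for this rule. The nearest stated figure is 80% power for a 0.532-point difference (SAP 6.2: N=1150, SD 2.85, 30% attrition). With 575/1.3 = 442 per arm the power is 79.3%, which agrees; with 575 × 0.7 = 402.5 it is 75.4%. This checks the inputs and has no bearing on the rule.

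**Algebra (no variance assumptions).** Let m(x) be the modelled Week 240 mean at exposure x. Placebo is exposure zero and there is no treatment term, so m(x) − m(0) = g(x), the exposure-spline contribution alone. The rule flags x when

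|ĝ(x)| > 1.96 × SE[m̂(x)].

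A 5% comparison needs 1.96 × SE[ĝ(x)]. With no exposure effect, the pointwise error of the rule is

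2 × (1 − Φ(1.96 × SE[m̂(x)] / SE[ĝ(x)])).

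This equals 5% only where the two standard errors are equal. As x approaches zero, SE[ĝ] goes to zero and SE[m̂] does not, so the ratio cannot be constant.

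**Numerical inputs.**
- From the documents: about 575 per arm, PACC every 24 weeks to Week 240, 30% attrition, SD of change 2.85 or 3.08, two-term splines for time and exposure.
- Assumed: baseline PACC SD, intercept-slope correlation 0 to 0.3, spread of escalation times, missed-infusion rate. Baseline covariates were left out.

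**One case** (baseline SD 2.6, SD of change 2.85, escalation spread over weeks 60-200):

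| Cumulative exposure | SE of mean | SE of difference | Ratio | Error of rule |
|---|---|---|---|---|
| 21.2 g (lowest observed) | 0.116 | 0.095 | 1.22 | 1.6% |
| 32.4 g | 0.118 | 0.118 | 1.00 | 4.9% |
| 40.0 g | 0.120 | 0.129 | 0.93 | 6.9% |
| 50.0 g | 0.125 | 0.143 | 0.88 | 8.6% |
| 59.2 g | 0.139 | 0.161 | 0.86 | 9.0% |
| 75.2 g (highest observed) | 0.186 | 0.209 | 0.89 | 8.1% |

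First row: 1.96 × 0.116/0.095 = 2.39, and 2 × (1 − Φ(2.39)) is about 1.7% from the rounded SEs (1.6% unrounded).

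**Range over assumptions.**

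| Exposure at Week 240 | Baseline SD 1.5-2.6 (variance 2.25-6.76) | Variance 3-10, three escalation spreads |
|---|---|---|
| Lowest observed | 0.4-5.5% | about 1-6% |
| 25th percentile | 4.7-12.0% | not tabulated |
| Median | 5.9-13.6% | about 5-11% |
| 75th percentile | 6.6-12.9% | not tabulated |
| Highest observed | 6.6-10.3% | about 6-11% |

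The top value, 13.6%, comes from baseline SD 1.5 with SD of change 3.08. SAP 5.1 makes the PACC a sum of four z-scores, so its unadjusted baseline variance is 4 + 12 × (mean correlation between components): 7 at a correlation of 0.25 and 10 at 0.5. Values below 4 require covariate adjustment to remove variance, so the upper end of the range is the less likely part.

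**Searching for the first crossing.** Under no effect, the chance that some exposure in the observed range is flagged, in either direction, is 10.8-19.6% with the rule as written and 9.8-10.8% with the pointwise interval of the difference.

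**The case against.** The strongest reply is about weight. This is a sensitivity analysis. SAP 7.4 makes every analysis except the primary PACC analysis secondary, and the sentence attaches no hypothesis, alpha or decision to the threshold. The exposure question does not rest on it: the same section compares the arms within exposure tertiles with a likelihood ratio test, and SAP 7.15 adds a weighted dose analysis. The placebo interval is also plotted over time, so its uncertainty is not hidden. All of this stands and limits the point to a minor one. It does not make the comparison correct.

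It is also true that the rates depend on inputs the documents do not give. Only the algebra is free of assumptions, and the lowest-exposure figure is particularly sensitive: with a small baseline variance the rule is already at about 5% there.

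Three stronger readings are tempting and not supported:

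- A reader might infer that the error simply rises with exposure. It does not: in the worked case it reaches 9.0% at 59.2 g and falls to 8.1% at 75.2 g.
- A reader might apply the familiar result for two independent means with equal standard errors, 2 × (1 − Φ(1.96/√2)) = 16.6%, or the roughly 13% from a two-group formula with correlation 0.5. Neither describes this model. The two means share an intercept and a time curve, the exposure enters as a spline, and SAP 6.2 gives the 0.5 within its Week 336 open-label calculation.
- A reader might take the threshold for a main result of the trial. The SAP does not present it as one.

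Reading the interval as already being that of the difference would remove the problem, but nothing in the section says so.

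**Conclusion.** Wrong as written; minor. The rule sets the interval of one modelled mean against another estimated mean, although the difference is available directly from the same fit. Its pointwise error is not held at 5% and varies with exposure; this follows from the model's form alone.

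The size depends on assumed baseline variances (about 2 to 10 across the two sets of calculations) and assumed escalation timing. On those, the error is roughly 1-6% at the lowest observed exposure and roughly 5-14% at median to high exposure. The likely harm is a misplaced threshold, biased upward where the rule is strict and too readily declared where it is loose. The primary test in SAP 7.9.1.1 is not touched.

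**What to change.** Keep the model and change the contrast. In SAP 7.9.1.2.4, replace the rule with the following: estimate the Week 240 difference from placebo (the exposure-spline contrast against exposure zero) with its 95% confidence interval over the observed exposure range, plot it, and report the lowest exposure at which that interval excludes zero.

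The difference interval restores 5% at each exposure but not over the search. Either label the threshold pointwise and descriptive, or use a simultaneous band if it is to bear more weight. SAP 7.9.3.4 extends the exposure model to the open-label data, so any similar readout there should use the same contrast.

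The cost is a sentence or two in the SAP, with no new data or model and no effect on the primary analysis. A simultaneous band would widen the intervals and could raise the reported minimum.
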